#### **14.4 Populations for Analyses**

- Modified Intention-to-Treat Analysis Dataset, Opioid Use: For the Day 7 analysis, this will include all randomized patients who have Day 7 opioid use assessed. For the Day 90 analysis, this will include all randomized patients who have Day 90 opioid use assessed.

- Modified Intention-to-Treat Analysis Dataset, Symptom Burden: This will include all randomized patients who have, at least, a valid baseline MDASI-BMT Total Symptom Severity score.
- Modified Intention-to-Treat Analysis Dataset, Other Continuous Endpoints: For a given continuous endpoint, this will include all randomized patients who have, at least, a valid baseline endpoint measurement.

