Patients and stakeholders took part in the formulation of the research question and the design of the study. We formed a Patient/Stakeholder Advisory Committee (PSAC) which consists of 3 patients who participated in the previous pilot study, a future HSCT patient, a patient caregiver, a representative from advocacy organization, 2 clinicians and 2 researchers. The PSAC helped with study design and development of patient-centered recruitment/retention strategies. One patient from the pilot study and one patient who is likely to receive HSCT in the near future will serve as consultants for the duration of the study.

The proposed study takes advantage of a highly efficient clinical pain model. Pain and other symptoms during HiChemo/HSCT follows a very predictable clinical course. This reduces variability and increases the statistical power of the study under a given sample size. It allows for a longitudinal evaluation of the transition from acute opioid use to chronic opioid use in each patient. The decision-making dilemma addressed by the study is commonly faced by patients and clinicians in clinical practice. The outcomes evaluated are all related to improving cancer care and patient-centered. The interventions are easy to implement. Patients, caregivers, clinicians and hospitals have a keen interest in incorporating non-drug-based pain management to reduced unnecessary opioid use. Such interest facilitates future dissemination of findings from this study. Thus, the proposed study will generate high quality evidence and potentially improve clinical practice.

[figure not shown]

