## **14.0 BIOSTATISTICS**

This is a multicenter, two-arm randomized controlled trial to compare the effects of two pain management strategies on opioid use, symptom burden, and other patient-reported outcomes among patients receiving high-dose chemotherapy (HiChemo) followed by HSCT. Opioid-naïve adult multiple myeloma, Hodgkin disease, and non-Hodgkin lymphoma patients undergoing HiChemo followed by HSCT will be randomized (at 1:1 ratio, see Section 7.2) to receive either acupuncture as a first-line pain preventive measure during HiChemo with opioids as back-up pain treatment (ACU), or opioids as first-line pain treatment (OPI). Study outcomes will be measured at pre-HiChemo baseline and at Days 7, 15, 30, and 90 after the first dose of HiChemo, with the Day 7 (short-term) and Day 90 (long-term) outcomes of particular interest. We expect to accrue approximately 12 patients per month, and we anticipate the study will be open to enrollment for approximately 30 months. We expect the

total study duration to be 3 years.

**14.1. Sample Size Considerations.** This study has 3 primary endpoints: opioid use at Day 7, opioid use at Day 90, and symptom burden at Day 7. The statistical plan takes that into consideration. Our overall Type I error rate for testing these 3 primary endpoints is set to alpha = 0.05. To maintain this Type I error rate, we will allocate alpha = 0.02 to each of the tests of opioid use at Day 7 and at Day 90, and we will allocate alpha = 0.01 to the test of symptom burden at Day 7.

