In our pilot study, among “opioid-naïve” patients, 25% of sham acupuncture (SA) patients and 7% of true acupuncture (TA) patients were opioid users at Day 90. For our sample size/power estimates for Aim 1, we conservatively assume that patients in the OPI arm will have similar Day 90 opioid usage (25%) as the SA patients in our prior study, and that 10% of patients in the ACU arm will be using opioids at Day 90 (slightly higher than the TA arm in our pilot study). This translates to a relative reduction of 60% fewer opioid users in the ACU arm, and an odds ratio of 0.33, which would be considered clinically meaningful. The attrition rate was only 5% in our pilot study. However, we will conservatively plan for a high 10% attrition rate by randomizing 300 patients (150 per arm) in order to obtain 270 patients (135 per arm) with evaluable Day 90 endpoints. With an initial sample size of 300 patients and a 10% attrition rate, we will have 81% statistical power to detect this Day 90 difference between the two arms (i.e. 10% vs 25%) at a significance threshold of  $p<0.02$  using logistic regression analysis and a two-sided significance test. It is possible that the OPI group will have higher opioid use than the SA patients in our pilot study, as sham acupuncture is known to have some placebo effect. We therefore expect a larger effect size than we observed in the pilot study where true acupuncture was compared to sham acupuncture. In that scenario, assuming 30% in the OPI group use opioids versus 10% in ACU group, our power will increase to 96%.

We based our sample size exclusively on having adequate power for the Day 90 comparison of opioid use. This was due to the high public health priority to find pain interventions that can reduce long-term opioid use. That said, we expect the Day 7 comparison to have similar power as the Day 90 comparison. We believe this is a conservative assumption, and that we most likely have higher power at Day 7 due to lower attrition and potentially a larger effect size at Day 7 relative to Day 90. For example, in our pilot study, 20% of sham acupuncture (SA) patients were using opioids at Day 5 (opioid usage not collected at Day 7) compared to none of the true acupuncture (TA) patients.

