## 14.2. Statistical Methods.

**14.2.1. General Approaches.** All analyses will be by intent-to-treat, with patients analyzed as randomized, irrespective of treatment actually received. Demographics and other relevant variables (e.g., number of acupuncture sessions received in the ACU arm) will be summarized by treatment arm using standard descriptive statistics. All data at all assessment time points will be summarized by treatment arm using standard descriptive statistics and plotted to visually assess trajectories over time. In the following subsections, we present specific analysis plans that are tailored to address our specific aim hypotheses, focus on single assessment time points, have relatively straightforward interpretations, and will be used to draw our primary conclusions regarding the Aims of this trial. However, our more general analysis approach will use more complex models to capitalize on the longitudinal nature of the study design and allow us to examine plots of the model-based trajectories of our outcome measures over time by study arm, giving us a visual overview of each outcome measure that incorporates all of the available data. For Aim 1, we will utilize generalized

linear mixed models (GLMM) to model the probability of opioid use across all time points (i.e. Day 7, 15, 30, and 90) as a function of study arm (ACU vs. OPI), time, the arm-by-time interaction, and randomization stratification variables.. For Aim 1 symptom burden, and for the continuous Aim 2 outcome measures, we will use linear mixed models (LMM) to similarly model those continuous endpoints over time. For both the GLMM and LMM analyses, we will use interaction terms between time and study arm to allow us to plot the arm-specific outcome trajectories over time. These statistical procedures (GLMM and LMM) account for within-subject correlations from repeated measurements in the same subjects and allow estimation of between-group differences without necessitating exclusion of participants with missing data.

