**14.2.2. Specific Aim 1 Analysis Methods.** To test Aim 1 hypotheses, we will test whether ACU has fewer opioid users compared to OPI at Day 7 (Hypothesis 1a) and at Day 90 (Hypothesis 1b) using separate but similar logistic regression models. Each model will predict opioid use at the given time point as a function of treatment arm (ACU vs. OPI), controlling for the randomization stratification variables (study site and cancer diagnosis). To test whether ACU reduces symptom burden at Day 7 compared to OPI (Hypothesis 1c), we will use a LMM to model the baseline and Day 7 MDASI-BMT Total Symptom Severity scores as a function of study arm (ACU vs. OPI), time (Day 0 and Day 7), and the arm-by-time interaction (coefficient of interest), controlling for the randomization stratification variables.

**14.2.3. Specific Aim 2 Analysis Methods.** For the Aim 2 hypotheses we will first test (Hypothesis 2a) whether mean pain scores among ACU patients were non-inferior to those among OPI patients (within a non-inferiority margin of 0.34 standard deviations) at Day 7 (key Aim 2 endpoint) using a LMM containing arm, time (Days 0 and 7), and the arm-by-time interaction as predictors, controlling for the randomization stratification factors. That is, if the mean Day 7 pain score in the ACU arm is not significantly ( $p < 0.025$ ) more than 0.34 standard deviations higher than the mean OPI pain score, then we will consider ACU to be non-inferior to OPI with respect to Day 7 pain control. A similar analysis will be performed for the Day 90 pain scores. For Hypothesis 2b, we will estimate mean differences (and 95% confidence intervals) between ACU vs. OPI side effect ratings, PROMIS-29 scores, and PROMS scores using separate linear mixed models for the Day 7 and Day 90 outcomes, controlling for the randomization stratification variables and baseline score (when relevant). We will have 80% power to detect unadjusted differences between study arms on these outcomes as small as 0.34 SD (i.e., Cohen's  $d = 0.34$ ) using two-sided tests and  $p < 0.05$ . By convention, this effect size is between a small (i.e.,  $d = 0.20$ ) and moderate ( $d = 0.50$ ) effect size. We will have power to detect smaller effect sizes in the covariate-adjusted regression analyses described above, but we have insufficient preliminary data on which to base estimates of these adjusted effect sizes.

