**14.3. Missing Data.** We will first explore whether missingness is associated with observed variables (particularly randomization arm and the baseline outcome measures) by comparing patients with complete and incomplete data. Of note, our general longitudinal data analysis approaches described above (GLMM and LMM) validly include patients with incomplete data under the missing at random assumption. However, our exploration of the data may deem the missing at random assumption to be inappropriate, and not all our hypotheses will be tested using these longitudinal modeling approaches. In these cases, we will use well-established methods such as multiple imputation and pattern mixture models to help us deal with these issues. We will perform sensitivity analyses to evaluate the robustness of our main findings by using multiple imputation to impute the missing outcomes (particularly for Day 7 and Day 90) and duplicating the analyses using the multiply imputed data sets.

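### The deciding Day 90 opioid test uses only patients assessed at Day 90 and ignores opioid use already recorded at Days 7, 15 and 30; the imputed analysis that would use it is a sensitivity analysis only

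*Combined protocol and SAP*

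**What the plan says.** Section 14.2.2 tests Hypotheses 1a and 1b with separate logistic models, one for Day 7 and one for Day 90, with arm and the stratification variables as the only predictors. Section 14.2.1 says that single-time-point analyses of this kind carry the primary conclusions. On the analysis set, 14.4 states: "For the Day 90 analysis, this will include all randomized patients who have Day 90 opioid use assessed". Section 13.2 defines evaluability in the same way.

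Opioid use is collected at Days 7, 15, 30 and 90 (Section 11.0). Section 3.0 presents this as a strength of the design: "It allows for a longitudinal evaluation of the transition from acute opioid use to chronic opioid use in each patient". A mixed model over all four visits is planned in 14.2.1. That section credits mixed models because they "allow estimation of between-group differences without necessitating exclusion of participants with missing data", but it gives this model the role of describing trajectories.

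Section 14.3 accepts that some hypotheses are not tested longitudinally and says that multiple imputation and pattern mixture models will help in such cases. It then promises sensitivity analyses "using multiple imputation to impute the missing outcomes (particularly for Day 7 and Day 90"). It does not list the variables in the imputation model, and it does not say that an imputed result would replace the complete-case one.

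On error control, 14.1 states: "we will allocate alpha = 0.02 to each of the tests of opioid use at Day 7 and at Day 90".

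**The concern.** A patient seen at Day 30 but missed at Day 90 drops out of the deciding test, although Day 30 use is likely to predict Day 90 use. The complete-case test is unbiased only if being missing is unrelated to Day 90 use given arm and stratification factors. The mixed models need only missingness at random given the recorded outcomes, which is a weaker condition.

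The plan is also uneven across its primary endpoints. For symptom burden, 14.4 keeps every randomised patient with a baseline score. For opioid use it keeps only those with the visit value.

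Two things are at stake at Day 90. Dropout linked to earlier use can shrink a real difference. If the link differs between arms, it can also create a difference where there is none. A difference by arm is possible because the control is usual care without sham (Section 4.1), so patients know their allocation.

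**Working it through.** **Inputs from the documents.** 150 randomised per arm; 10% attrition, so 135 evaluable per arm; Day 90 use 25% (OPI) against 10% (ACU); threshold p<0.02, "using logistic regression analysis and a two-sided significance test"; stated power 81% (all Section 14.1). Pilot sham use in opioid-naïve patients was 40% around Day 30 and 25% at Day 90 (Section 3.0).

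**Assumptions, not in the documents.** ACU Day 30 use of 12% under the planned effect; Day 30/Day 90 latent-normal correlation of 0.6-0.8; dropout before Day 90 that depends on Day 30 use.

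**Step 1: the plan's own power.** Two proportions, n = 135 per arm, z = 2.326:
- null standard error = √(2 × 0.175 × 0.825 / 135) = 0.0463
- alternative standard error = √((0.25 × 0.75 + 0.10 × 0.90) / 135) = 0.0453
- power = Φ[(0.15 − 2.326 × 0.0463) / 0.0453] ≈ Φ(0.935) = 82.5%

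A Wald log-odds formula gives 79.4%. The stated 81% is sound. It assumes loss unrelated to use.

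**Step 2: complete-case rate.** Let a be the proportion using opioids at both Day 30 and Day 90 (from the bivariate normal), and let d_u and d_n be the dropout rates of Day 30 users and non-users. Then

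rate = [a(1 − d_u) + (p90 − a)(1 − d_n)] / [p30(1 − d_u) + (1 − p30)(1 − d_n)].

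**Step 3: planned effect, same pattern in both arms** (d_u = 25%, d_n = 5%, correlation 0.7):
- OPI, a = 0.197: (0.197 × 0.75 + 0.053 × 0.95) / (0.40 × 0.75 + 0.60 × 0.95) = 0.198 / 0.870 = 22.8%
- ACU, a = 0.0523: (0.0523 × 0.75 + 0.0477 × 0.95) / (0.12 × 0.75 + 0.88 × 0.95) = 0.0845 / 0.926 = 9.1%

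The difference is about 13.6 points instead of 15. Over correlations 0.6-0.8 it is about 13.4-13.8 points, with power about 77-78%. Random loss gives about 83%. In simulation, imputing from Day 7 and Day 30 use gave 81% against 78% complete-case under this pattern, and 84% against 83% under random loss.

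**Step 4: no true effect, same pattern in both arms.** With equal earlier use, both arms shift equally. Rejection stays at about 0.019-0.020, so the 0.02 rate holds.

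**Step 5: no true effect, pattern in ACU only** (40% and 25% use in both arms, OPI losing 10% at random):
- Steep (d_u = 25%, d_n = 3%, correlation 0.7): (0.197 × 0.75 + 0.053 × 0.97) / (0.40 × 0.75 + 0.60 × 0.97) = 0.199 / 0.882 = 22.6% instead of 25%. The 0.02 test rejects about 3.2-3.5% of the time depending on method, and about 3-4% over correlations 0.6-0.8.
- Moderate (users lost at about 2 to 4 times the rate of non-users, about 10% attrition): about 1.9-2.9%.
- With imputation from Day 7 and Day 30 use, simulated rejection in the steep case was 2.0%, against 3.5% complete-case.

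**Step 6: independent check with Day 7 use as the driver of dropout** (100,000 simulated trials per scenario):

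| Pattern at 10% attrition, no true effect | Complete-case rejection |
|---|---|
| Use-related dropout in ACU only | 0.021-0.025 |
| Opposite patterns in the two arms | 0.019-0.039 |
| All ACU losses among users, OPI random | 0.056 |
| All ACU losses among users, all OPI losses among non-users | 0.100 |

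An estimator that uses Day 7 use within arm held 0.020-0.022 in every scenario. Its power was 84.8% against 82.7% with random loss, and 82.4% against 80.5% with users lost four times as often in both arms.

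**The case against.** Much of this is already provided for. Section 14.3 foresees imputation for hypotheses outside the longitudinal models, and 14.2.1 plans a mixed model over all four visits. Retention is protected: patients who stop the intervention stay in for outcomes, those who withdraw are followed with permission (Section 12.0), and pill counts can be remote (Section 13.1). Pilot attrition was only 5% (Section 14.1). These points stand, and they reduce the issue to which planned analysis decides. They do not settle it, because 14.4 restricts the Day 90 set to assessed patients and the only explicit commitment to imputing Day 90 is labelled a sensitivity analysis.

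A reader might infer that any dropout tracking earlier use breaks the 0.02 error rate. It does not: Step 4 shows the rate intact when both arms share the pattern and the same earlier use. Nor is the direction fixed, since the mirror pattern would work against ACU.

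A reader might also extend the point equally to Day 7. The documents do not support that. Day 7 is the first post-baseline visit, patients are not regular opioid users at entry (Section 6.1), and 14.1 expects lower attrition there. Only later visits could inform a missing Day 7 value, and no Day 7 bias was calculated.

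Finally, the gain from imputation is shown at its best, because the simulated imputation model contains the variable that drives dropout. Patients lost before Day 30, or lost because of current use, benefit less.

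**Conclusion.** The concern holds for Day 90 and is moderate in size. The deciding test leaves out recorded opioid data that could remove part of the dropout bias. Under a shared, fairly strong dropout pattern, the cost is about 1.2-1.6 points of the 15-point difference and about 5-6 points of power relative to random loss; imputation recovers about 1-3 points of power. Inflation of the 0.02 rate is conditional on arm-specific dropout. It is slight for moderate patterns and reaches about 3-4% for steep ones at about 10-12% attrition; only extreme patterns go further. All of this depends on the assumed correlation and dropout rates. The stated 81% power is not in error, and the point carries little weight for Day 7.

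**What to change.** In 14.2.2, 14.3 and 14.4, with 13.2 brought into line:
- Name the already planned multiply imputed analysis as primary for Day 90 opioid use, and for Day 7 for consistency.
- Include all randomised patients. Impute with arm, opioid use at all post-baseline visits, and the stratification factors. Keep arm-specific terms simple, since only about 15 ACU users are expected at Day 90 (10% of 150).
- Fit the same logistic model, combine by Rubin's rules, and keep p<0.02.
- Keep the complete-case analysis as a sensitivity analysis.
- Do not impute opioid use after death. Tabulate deaths by arm; Section 11.0 already collects mortality.

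The cost is SAP wording and the work of specifying the imputation model in advance. No new data, patients or threshold are needed. The downside is small: the primary result then depends on that pre-stated model, and it corrects only for dropout explained by recorded data.

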## 7.2 Randomization

After registration, research staff will randomize patients via MSK's secure Clinical Research Database (CRDB) using permuted blocks of random length. The allocation ratio will be 1:1 for ACU:OPI. Using the institutional randomization standard procedure with random blocks for RCTs will ensure full allocation concealment. Randomization will be stratified by study site, primary cancer diagnosis (MM versus HD versus NHL) and transplantation setting (inpatient versus outpatient) to ensure these characteristics are comparably distributed between the two study arms.

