## 9.0 PRE-TREATMENT/INTERVENTION

Enrolled patients will receive the following baseline assessments within 4 weeks before the first dose of HiChemo. Detailed descriptions of each assessment are in Section 11.0 and 13.1.

- Demographic and Clinical Features
- Symptom Burden (MDASI-BMT), paper or electronic
- Brief Pain Inventory – Short Form (BPI), paper or electronic
- Patient-Reported Oral Mucositis Symptom Scale (PROMS) ,paper or electronic
- Pain Medication Side Effects Questionnaire,paper or electronic
- Quality of Life (PROMIS-29), paper or electronic
- Adverse Events (CTCAE v5)
- Opioid Risk Tool (ORT), paper or electronic
- Acupuncture Expectancy Scale (AES), paper or electronic

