### **13.2 Criteria for Study Endpoint Evaluability**

All patients who are randomized and who have their opioid use evaluated at Day 7 will be considered evaluable for the Day 7 opioid primary endpoint. Similarly, patients who have their opioid use evaluated at Day 90 will be evaluable for the Day 90 opioid primary endpoint. For the Day 7 symptom burden primary endpoint, all patients who are randomized and who have at least a baseline MDASI-BMT Total Symptom Severity score will be considered evaluable. In general, patients will be considered evaluable for continuous study endpoints as long as they have at least the baseline measurement. No patient will be replaced after randomization. All randomized patients meeting these additional evaluability criteria will be included in the analyses using the modified intention-to-treat (ITT) principle (i.e. participants will be analyzed according to the treatment group to which they will be randomly allocated regardless of treatment adherence status).

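### Sections 13.2 and 14.4 drop randomised patients without a baseline score from the continuous endpoints, even when their follow-up score was observed

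*Combined protocol and SAP*

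**What the plan says.** **Analysis sets.** For symptom burden, section 14.4 states: "This will include all randomized patients who have, at least, a valid baseline MDASI-BMT Total Symptom Severity score". For every other continuous endpoint, "this will include all randomized patients who have, at least, a valid baseline endpoint measurement". Section 13.2 gives the matching evaluability rule: "patients will be considered evaluable for continuous study endpoints as long as they have at least the baseline measurement". Both sections call the result a modified intention-to-treat set.

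**General principle.** Section 14.2.1 says that all analyses are by intent-to-treat, with no qualifier, and that the mixed models "allow estimation of between-group differences without necessitating exclusion of participants with missing data". Section 14.3 adds that these models validly include incomplete patients under missing at random.

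**Models.** For hypothesis 1c, section 14.2.2 says "we will use a LMM to model the baseline and Day 7 MDASI-BMT Total Symptom Severity scores as a function of study arm", with the arm-by-time interaction as the coefficient of interest. For 2a, section 14.2.3 tests non-inferiority "using a LMM containing arm, time (Days 0 and 7), and the arm-by-time interaction as predictors". For 2b, the baseline score is a covariate where relevant.

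**Timing.** Section 7.2: "After registration, research staff will randomize patients". Section 9.0: "Enrolled patients will receive the following baseline assessments within 4 weeks before the first dose of HiChemo". Section 6.1 admits patients whose high-dose chemotherapy is up to 30 days away. Section 4.1 makes the control usual care without sham, so patients know their arm.

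**The concern.** Two things do not fit together. The plan promises intent-to-treat and chooses models that can use a patient seen only at follow-up, yet its analysis sets remove that patient. In the 1c and 2a models the baseline score sits in the outcome vector, so a patient with only a Day 7 score still informs the Day 7 mean. Nothing in those models forces the exclusion, and no reason is given.

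The removal also turns on a self-report form whose order relative to randomisation is not fixed. If some patients complete it, or fail to, after learning their arm, the exclusion happens after randomisation and can differ by arm. At stake are one of the three primary endpoints and the non-inferiority test on pain. The compared groups would no longer be quite the randomised groups, and observed follow-up scores would be discarded.

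**Working it through.** **Inputs (section 14.1).** 150 per arm, 10% attrition, correlation ρ = 0.50 between baseline and Day 7, two-sided alpha 0.01, power 80%, stated detectable effect 0.41. Scores are scaled to SD 1, so the SD of change is √[2(1 − 0.50)] = 1. The share lacking a baseline is not in the documents; 2%, 5% and 10% are assumptions, equal in both arms and independent of attrition.

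**1. Reproduce 0.41.** Per arm, 135 patients have both scores and 15 have baseline only. With ρ = 0.50 the inverse correlation matrix is [[4/3, −2/3], [−2/3, 4/3]], so the information on the baseline and Day 7 means is [[195, −90], [−90, 180]], with determinant 27,000. Hence Var(baseline) = 180/27,000, Var(Day 7) = 195/27,000, covariance = 90/27,000, and Var(change) = (180 + 195 − 180)/27,000 = 0.007222. Detectable effect = (2.576 + 0.842) × √(2 × 0.007222) = 0.411. The plan's figure reproduces; it assumes that all 150 per arm have a baseline.

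**2. Drop patients without baseline.** All counts scale by (1 − m), so the detectable effect is 0.4107/√(1 − m).

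**3. Keep them.** With m = 10%, each arm has 121.5 patients with both scores, 13.5 with baseline only and 13.5 with Day 7 only. Information = [[175.5, −81], [−81, 175.5]], with determinant 24,239.25. Var(change) = 2 × (175.5 − 81)/24,239.25 = 0.007797, giving 0.427. Var(Day 7) = 175.5/24,239.25 = 0.007240, giving 0.411.

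| Lacking baseline | Dropped (plan) | Kept, arm-by-time coefficient | Kept, Day 7 mean difference |
|---|---|---|---|
| 2% | 0.415 | 0.414 | 0.411 |
| 5% | 0.421 | 0.418 | 0.411 |
| 10% | 0.433 | 0.427 | 0.411 |

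Power at 0.41 falls from 79.8% to 78.9%, 77.3% and 74.6% when they are dropped. Keeping them gives 79.1%, 78.0% and 76.0% on the coefficient, and 79.7% to 79.8% on the Day 7 mean difference.

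**4. Selection, illustrated.** Assume no true effect. Baseline is missing in 10% of OPI patients, all with above-average baseline scores, and in no ACU patients. For simplicity, take Day 7 as complete.
- The mean of a standard normal above zero is √(2/π) = 0.798. The 90% of OPI patients retained have mean baseline −0.1 × 0.798/0.9 = −0.0887 and mean Day 7 score 0.50 × −0.0887 = −0.0443.
- Dropped: Day 7 mean difference (ACU − OPI) = 0 − (−0.0443) = +0.044. Arm-by-time coefficient = 0 − (−0.0443 + 0.0887) = −0.044.
- Kept: every OPI Day 7 score is used, so that mean is 0 and the Day 7 difference is 0. The model estimates the OPI baseline mean as −0.0887 + 0.50 × (0 + 0.0443) = −0.0665, so the coefficient is 0 − (0 + 0.0665) = −0.0665.

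A simulation with 10% Day 7 attrition agrees: the mean difference is +0.046 dropped and +0.003 kept; the coefficient is −0.046 dropped and −0.069 kept.

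**The case against.** The best defence is that the sets are prespecified and openly labelled as modified. Requiring a baseline for a change-from-baseline contrast is a common convention, and the sentence in 14.2.1 describes a property of mixed models without defining a population. Section 14.3 compares complete with incomplete patients, by arm among other variables, and plans multiple imputation of missing outcomes. The precision at issue is slight: on the planned coefficient, keeping these patients improves the detectable effect by only 0.001 to 0.006 SD, and every value in the table stays below the 0.50 SD that section 14.1 takes as clinically important.

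Much of this stands, and it makes the point minor. It does not close it. Section 14.2.1 claims intent-to-treat for all analyses, and 14.3 nowhere says that patients excluded for a missing baseline are restored.

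Three stronger readings are tempting and are not supported:
- A reader might infer that baseline does follow allocation, because the section 11.0 table marks the Acupuncture Expectancy Scale as completed by ACU patients. But section 9.0 lists that scale for all enrolled patients, 13.1 sets no arm limit, and 14.2.5 plans its interaction with arm, which needs it in both arms. The table cell may be an error, and it says nothing about when the MDASI-BMT is completed. The order is unspecified, no more.
- A reader might infer that widening the set has no downside. Step 4 shows otherwise: with arm-dependent missingness, the planned coefficient is more biased with these patients kept.
- A reader might infer that the endpoint is materially underpowered. No expected share of missing baselines is given, and the loss is small across the assumed range.

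**Conclusion.** The concern holds as a minor inconsistency with an inexpensive remedy. The baseline requirement conflicts with the stated intent-to-treat principle, and the 1c and 2a models do not need it. For 2b a missing baseline covariate would remove the patient unless imputed.

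The precision cost is a detectable effect of 0.415 to 0.433 SD against 0.411, if 2% to 10% lack a baseline. The possible selection effect matters more but cannot be sized from the documents. In the illustration it is 0.044 SD under the plan, about 11% of the 0.41 detectable effect (0.044/0.41). It is also about 13% of the 0.34 SD non-inferiority margin (0.044/0.34), if pain behaves alike. That scenario is deliberately one-sided; the sign reverses if the missing forms are in the ACU arm, and the effect vanishes if missingness is unrelated to arm and score. The near-zero bias of the Day 7 mean difference with patients kept assumes that Day 7 attrition is not itself selective.

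**What to change.** 1. In 13.2 and 14.4, define each continuous-endpoint set as all randomised patients with a baseline score or a score at the analysed follow-up. Use one term, intent-to-treat or modified, consistently with 14.2.1.
2. For 1c and 2a, name as the contrast the between-arm mean difference at Day 7 (Day 90 for the later pain test), estimated from the mixed model in that set. This matches hypothesis 1(c) in section 2.0, which concerns the Day 7 score, and 14.2.3, which already describes 2a in terms of Day 7 means. Report the baseline-required set as a sensitivity analysis. Forcing a common baseline mean instead is not a full answer: in the step 4 scenario it leaves about −0.03 SD with these patients kept.
3. For 2b, impute a missing baseline covariate; do not drop the patient.
4. In 7.2 or 9.0, state that baseline patient-reported forms are completed before randomisation. Report missing baselines by arm and, for patients already randomised, form dates against allocation dates.

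Cost: short text edits, one extra sensitivity analysis and a changed contrast for a primary endpoint. Precision is about equal at the assumed correlation of 0.50. With complete data, the variance of the change contrast relative to the Day 7 contrast is 2(1 − ρ): 1.0 at 0.50, 1.2 at 0.40 and 0.8 at 0.60. A correlation above 0.50 would therefore make the new contrast somewhat less precise. The change should be made before outcome data are examined by arm.
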